8.9.3. Unscheduled Reactogenicity Visits for a Grade 3 or Suspected Grade 4 Reaction

If a **severe** local reaction ([Section 8.2.4.1](#)), **severe** systemic event ([Section 8.2.4.2](#)), or fever $\geq 39.0^{\circ}\text{C}$ ($\geq 102.1^{\circ}\text{F}$) ([Section 8.2.4.3](#)) is reported in the e-diary, a telephone contact should occur to ascertain further details and determine whether a site visit is clinically indicated. If a suspected Grade 4 local reaction, systemic event, or fever is reported in the reactogenicity e-diary, a telephone contact or site visit should occur to confirm whether the event meets the criteria for Grade 4.

A site visit or referral to a healthcare facility should be scheduled as soon as possible to assess the extent of the reaction, unless:

- The participant is unable to attend the unscheduled visit, or
- The reaction is no longer present at the time of the contact, or
- The participant recorded an incorrect value in the e-diary (confirmation of an e-diary data entry error), or
- The investigator or appropriate designee determines that an unscheduled visit ([Section 8.9.3](#)) is not required.

This contact will be recorded in the participant's source notes and in the CRF.

Any ongoing reactions must be assessed at the next scheduled visit.

The reactogenicity events should be assessed by the investigator or a medically qualified member of the site staff such as a study physician or a study nurse, as applicable to the investigator's local practice or healthcare facility, who will:

- Measure body temperature and record any fever ([Table 3](#)).
- If present, measure the minimum and maximum diameters of redness at the injection site.
- If present, measure the minimum and maximum diameters of swelling at the injection site.
- Assess any injection site pain in accordance with the reactogenicity grading scale provided in [Table 1](#).
- Assess any systemic events (fatigue, headache, vomiting, nausea, diarrhea, muscle pain, or joint pain) that are present in accordance with the reactogenicity grading scale provided in [Table 2](#).
- Assess for other findings associated with the reaction and record on the AE page of the CRF, if appropriate.
- Record AEs and SAEs as described in [Section 8.3.1.2](#).
- Complete the participant's source documents.
- The investigator or an authorized designee will complete the unscheduled-visit-assessment CRF.

9. STATISTICAL CONSIDERATIONS

Methodology for summary and statistical analyses of the data collected in this study is described here and further detailed in the SAP, which will be maintained by the sponsor. The SAP may modify what is outlined in the protocol where appropriate; however, any major modifications of the primary endpoint definitions or their analyses will also be reflected in a protocol amendment.

9.1. Statistical Hypotheses

9.1.1. Estimands

The estimands corresponding to each primary [CCI](#) objective are described in [Section 3](#).

The estimands to evaluate the immunogenicity objectives are based on the evaluable immunogenicity population ([Section 9.2](#)). These estimands estimate the vaccine effect in the hypothetical settings where participants follow the study schedules and protocol requirements as directed. Missing serology results will not be imputed, as MCAR is assumed.

In the primary safety objective evaluations, completely missing reactogenicity e-diary data will not be imputed. Missing AE dates will be imputed according to Pfizer safety rules. No other missing information will be imputed in the safety analysis.

9.1.2. Statistical Hypotheses

This study has 1 primary immunogenicity objective, which is to demonstrate that the immune responses for RSV A and RSV B induced by 3 lots of RSVpreF are equivalent. The objective will be evaluated at 1 month after vaccination for RSV A and RSV B using the evaluable immunogenicity population.

The null hypothesis (H_0) for lot consistency for RSV A and RSV B is as follows:

$$H_0: |\ln(\mu_1) - \ln(\mu_2)| \geq \ln(1.5) \text{ or } |\ln(\mu_1) - \ln(\mu_3)| \geq \ln(1.5) \text{ or } |\ln(\mu_2) - \ln(\mu_3)| \geq \ln(1.5)$$

where $\ln(1.5)$ corresponds to a 1.5-fold equivalence margin, and $\ln(\mu_1)$, $\ln(\mu_2)$, and $\ln(\mu_3)$ are the natural log of the geometric mean of RSV antigen-specific NTs from participants receiving RSVpreF in Group 1, Group 2, and Group 3, respectively, measured 1 month after vaccination.

Lot consistency will be declared if the 2-sided 95% CI for the ratio of GMTs for every pair of RSVpreF lots is contained in the interval (0.667, 1.5), for both antigens simultaneously.

9.1.3. Multiplicity Adjustment

No multiplicity adjustment will be applied for this study. The primary objective of equivalence will be achieved only if the 1.5-fold equivalence criterion is met for every pair of between-lot comparisons from 3 lots and for both RSV A and RSV B antigens simultaneously. Each of the 6 statistical tests (3 pairwise comparisons between lots \times 2 RSV antigens) will use a 2-sided alpha level of 0.05.

9.2. Analysis Sets

Population	Description
Enrolled	All participants who sign the ICD.
Randomly assigned to study intervention	All participants who are assigned a randomization number in the IRT system.
Evaluable immunogenicity	All participants who are eligible, receive the study intervention to which they were randomized, have valid and determinate immunogenicity result from the blood sample collected within an appropriate window at 1 month after vaccination, and have no major protocol violations.
mITT	All randomized participants who receive study intervention and have at least 1 valid and determinate assay result after vaccination.
Safety	All randomized participants who receive study intervention.

9.3. Statistical Analyses

The SAP will be developed and finalized before any analyses are performed and will describe the analyses and procedures for accounting for missing, unused, and spurious data. This section is a summary of the planned statistical analyses of the primary and secondary endpoints.

9.3.1. General Considerations

Unless stated otherwise, “vaccine group” in this section refers to participants receiving any 1 of the 3 RSVpref lots or placebo. CIs for all endpoints in the statistical analysis will be presented as 2-sided at the 95% level unless specified otherwise.

For all the immunogenicity endpoints, the analysis will be based on the evaluable immunogenicity population. An additional analysis will be performed based on the mITT population if there is a large enough difference in sample size between the mITT population and the evaluable immunogenicity population. Participants will be summarized according to the vaccine group to which they were randomized.

The safety analyses will be based on the safety population. Participants will be summarized by vaccine group according to the study interventions they actually received.

9.3.1.1. Analyses for Binary Data

Descriptive statistics for categorical variables (eg, proportions) are the percentage (%), the numerator (n) and the denominator (N) used in the percentage calculation, and the 95% CIs where applicable.

The exact 95% CI for binary endpoints for each group will be computed using the F distribution (Clopper-Pearson).

9.3.1.2. Analyses for Continuous Data

Unless otherwise stated, descriptive statistics for continuous variables are n, mean, median, SD, minimum, and maximum.

9.3.1.2.1. Geometric Mean Ratios

[figure not shown]
The GMRs will be calculated as the mean of the difference of logarithmically transformed assay results between 2 vaccine groups and exponentiating the mean. Two-sided CIs will be obtained by calculating CIs using Student’s t-distribution for the mean difference of the logarithmically transformed assay results and exponentiating the confidence limits.

9.3.1.2.2. Geometric Means

The geometric means will be calculated as the mean of the assay results after making the logarithm transformation and then exponentiating the mean to express results on the original scale. Two-sided 95% CIs will be obtained by taking log transforms of assay results,

calculating the 95% CI with reference to Student's t-distribution, and then exponentiating the confidence limits.

CCI

9.3.2. Primary Endpoint(s)

[figure not shown]
Endpoint	Statistical Analysis Methods
Immunogenicity	
GMRs of RSV NTs for each between-lot comparison (Group 1/Group 2, Group 1/Group 3, and Group 2/Group 3) for RSV A and RSV B at 1 month after vaccination will be provided along with associated 2-sided 95% CIs (Section 9.3.1.2.1).
 
Using a 1.5-fold equivalence margin, lot consistency will be declared if the 2-sided 95% CI for each GMR is contained in the interval (0.667, 1.5).

Endpoint	Statistical Analysis Methods
Safety	
Descriptive statistics will be provided for each reactogenicity endpoint in the pooled RSVpreF lots (Groups 1, 2, and 3) and placebo. Local reactions (redness, swelling, and pain at the injection site) and systemic events (fever, fatigue, headache, vomiting, nausea, diarrhea, muscle pain, and joint pain) from Day 1 through Day 7 after vaccination will be presented by severity and cumulatively across severity levels.
 
Descriptive summary statistics will include counts and percentages of participants with the indicated endpoint and the associated Clopper-Pearson 95% CIs (Section 9.3.1.1).
 
AEs and SAEs will be categorized according to MedDRA terms. Counts, percentages, and the associated Clopper-Pearson 95% CIs of AEs and SAEs after vaccination will be provided for the pooled RSVpreF lots and placebo.
 
A 3-tier approach will be used to summarize AEs. For both Tier 1 and Tier 2 events, the 95% CIs for the difference in percentage of participants reporting the events between the pooled RSVpreF lots and placebo will be calculated using the test statistic proposed by Miettinen and Nurminen;²² in addition, for Tier 1 events, the asymptotic p-values will also be presented for the difference in percentage of participants reporting the events, based on the same test statistic and under the assumption that the test statistic is asymptotically normally distributed. There is no preidentified Tier 1 event for this study. A MedDRA preferred term is defined as a Tier 2 event if its incidence is at least 1% in the pooled RSVpreF group or in the placebo group.

9.3.3. Secondary Endpoint(s)

Not applicable.

CCI

9.4. Interim Analyses

No formal interim analysis will be conducted for this study. Only 1 analysis will be performed at the completion of the study.

9.5. Sample Size Determination

Table 4 presents the power to demonstrate that the immune responses induced by 3 lots of RSVpreF are equivalent in regard to the 2 RSV antigens.

Pairwise lot-consistency comparisons will be based on the GMRs and the corresponding 95% CIs. For both antigens, it is assumed that true differences between lots are not larger than 0 (on the natural log scale). The SDs of the log titers for RSV A and RSV B are based on Study C3671001 data.

With 225 evaluable participants per vaccine group and the above assumptions, the power is 93.3% for declaring the overall equivalence of the 3 RSVpreF lots for both RSV A and RSV B.

Allowing for a nonevaluable rate of approximately 10%, up to 1000 participants will be enrolled in the study to provide the required sample size of approximately 900 participants for the evaluable population analysis. Participants who withdraw or are withdrawn from the study after randomization will not be replaced, regardless of the reason for withdrawal.

Table 4. Power for the Primary Immunogenicity Objective (Lot Consistency)

Endpoint	Within-Lot SD (Log Scale) ^a	Maximum Lot Difference (Log Scale)	Consistency Margin	Number of Evaluable Participants per Vaccine Group	Power to Declare Consistency ^b
RSV A	0.96	0	1.5-fold	225	98.5%
RSV B	1.07	0	1.5-fold	225	94.7%
Overall power to declare consistency for RSV A and RSV B simultaneously					93.3%

a. The reference study is C3671001.

b. The power to declare equivalence between all 3 pairwise comparisons assuming a mean difference of 0 between any 2 RSVpreF lots, at a 0.05 alpha level (2-sided).

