6. ANALYSES AND SUMMARIES

6.1. Primary Endpoints

6.1.1. Primary Immunogenicity Endpoint

6.1.1.1. RSV A– and RSV B–Neutralizing Titers Measured 1 Month After Vaccination

6.1.1.1.1. Main Analysis

- Estimand strategy: Hypothetical ([Section 2.1.1.1](#)).
- Analysis set: Evaluable immunogenicity population ([Section 4](#)).
- Analysis methodology: GMRs of RSV A–neutralizing titers for each between-lot comparison and GMRs of RSV B–neutralizing titers for each between-lot comparison (Group 1/Group 2, Group 1/Group 3, and Group 2/Group 3) at 1 month after vaccination will be provided along with associated 2-sided 95% CIs ([Section 5.2.2.3](#)).
- Intercurrent events and missing data: Data collected after an intercurrent event will not be included. Missing data will not be imputed.
- Lot consistency will be declared if the 2-sided 95% CI for each GMR is contained in the interval (0.667, 1.5).
- A forest plot with GMRs of each between-lot comparison and the associated 95% CI for RSV A and RSV B will be presented.

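### Protocol Table 4 overstates power: with 225 per lot and the plan's 95% CI rule, RSV B power is 90.0% (stated 94.7%) and overall power is 87–90% (stated 93.3%)

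*Protocol*

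**What the plan says.** Table 4 in Protocol 9.5 reports power of 98.5% for RSV A, 94.7% for RSV B and 93.3% for both together. The text above it repeats the last figure: "With 225 evaluable participants per vaccine group and the above assumptions, the power is 93.3% for declaring the overall equivalence". Footnote b defines the per-antigen figure as "The power to declare equivalence between all 3 pairwise comparisons assuming a mean difference of 0 between any 2 RSVpreF lots", at a 2-sided alpha of 0.05.

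The test that these figures should describe is the same wherever it is stated:

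- Protocol 9.5: "Pairwise lot-consistency comparisons will be based on the GMRs and the corresponding 95% CIs".
- Protocol 9.1.2: "Lot consistency will be declared if the 2-sided 95% CI for the ratio of GMTs for every pair of RSVpreF lots is contained" in (0.667, 1.5), for both antigens.
- Protocol 9.1.3: each of the six tests "will use a 2-sided alpha level of 0.05".
- SAP 5.1.1, 5.1.2 and 6.1.1.1.1 repeat the rule with the same level and limits.
- Protocol 9.3.1.2.1 and SAP 5.2.2.3 base the interval on Student's t for log titers.

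No other confidence level is given for the lot comparison.

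**The concern.** Table 4 is the only power statement for the single primary immunogenicity hypothesis. The SAP version history records that the sample size and the consistency threshold were changed after CBER feedback, so the table supports the amended design. Success needs all six comparisons to pass, which makes the result sensitive to the antigen with the larger SD, RSV B.

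If the table is too high, the sponsor is carrying more risk of a failed primary objective than the protocol shows. The assumed true difference of 0 is also the most favourable case, so any real difference between lots would lower power further.

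**Working it through.** **Inputs (Protocol 9.5 and 9.1.2).** n = 225 evaluable per lot; SD 0.96 (A) and 1.07 (B); true difference 0; margin ln 1.5 = 0.4055; 2-sided 95% CI for each of three pairs. The correlation between the RSV A and RSV B titers is not given, so I vary it from 0 to 1.

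**Step 1: can the stated figures be reproduced?** The overall figure is the product of the two rows: 0.985 × 0.947 = 0.933. That is what independent antigens would give.

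The two rows cannot be obtained from a 95% CI. They come out closely if each limit is tested at one-sided 0.05, which is a 90% CI. Single-pair power with the t interval is then 0.9953 (A) and 0.9821 (B).

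- Cubed for three pairs: 0.9953³ = 98.6% and 0.9821³ = 94.7%; product 93.4%.
- Bonferroni bound, 1 − 3(1 − p): 98.6% and 94.6%; product 93.3%.

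This suggests how the table may have been made, but it is an inference. The documents do not give the method.

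**Step 2: power under the plan's rule.** With equal lot sizes and a common SE, all three pairs pass when the range of the three lot means is below ln 1.5 − t × SE. Here SE = SD × √(2/225) and t(448, 0.975) = 1.965. Dividing by SD/√225 gives a limit c. The power is then the distribution function of the range of three standard normals:

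P(range < c) = 3 ∫ φ(x) [Φ(x + c) − Φ(x)]² dx

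| | RSV A | RSV B |
|---|---|---|
| SE of a pair | 0.0905 | 0.1009 |
| t × SE | 0.1779 | 0.1983 |
| 0.4055 − t × SE | 0.2276 | 0.2072 |
| SD/√225 | 0.0640 | 0.07133 |
| c | 3.556 | 2.905 |
| **Power, all three pairs** | **96.8%** | **90.0%** |
| Stated in Table 4 | 98.5% | 94.7% |

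Allowing for estimated variances does not change these figures. A simulation of 400,000 trials with pairwise t intervals agrees (A 96.8%, B 90.0%). Using 0.667 instead of 1/1.5 as the lower limit has a negligible effect.

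**Step 3: both antigens together.**

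| Correlation between antigens | Overall power |
|---|---|
| 0 | 87.1% |
| 0.5 | 87.7% |
| 0.8 | 88.9% |
| 0.9 | 89.5% |
| 1 (ceiling = RSV B power) | 90.0% |

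The shortfall against 93.3% is 93.3 − 90.0 = 3.3 points at best, and 93.3 − 87.1 = 6.2 points under independence.

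**Step 4: other explanations tried.**

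- *Rounding of the SDs.* At the low end of rounding (0.955 and 1.065), RSV B is 90.3% and overall power is 87.5% under independence. Reaching 94.7% for RSV B needs an SD of about 1.00.
- *A simpler way of combining pairs at the 95% level.* Single-pair power is 98.8% (A) and 96.0% (B). Cubing gives 96.4%, 88.4% and 85.2% overall; Bonferroni gives 96.4%, 87.9% and 84.7%. Both move further from the table.
- *All 250 randomized per lot counted as evaluable.* This gives 98.4%, 94.0% and 92.5%. It is closer but still below the stated values, and the table says 225.
- *Only one confidence limit per pair counted, then cubed.* This gives 98.2%, 94.2% and 92.5%. It is not the two-sided rule and does not match either.
- *Sample size needed.* RSV B reaches 94.7% at 256 evaluable per lot. At that size overall power under independence is 93.4%. This is more than the 250 to be randomized per lot.

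**The case against.** The strongest case is that this is a planning figure and nothing in the analysis depends on it. The hypotheses, margin, CI rule and analysis set are consistent across both documents, and no conclusion of the trial would change. Power of 87–90% is still respectable. The gap is also comparable to the uncertainty in an SD borrowed from Study C3671001: an RSV B SD of about 1.00 instead of 1.07 would restore 94.7%.

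This limits the consequences. It does not make the table right for the SD it states.

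Three narrower points stand:

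- The RSV A gap is 98.5 − 96.8 = 1.7 points. It is small and would not justify a correction alone; the material errors are RSV B and the overall figure.
- Because the stated overall figure equals the product of the two rows, the like-for-like replacement is about 87%. The 90% figure is an upper bound that requires perfect correlation.
- The documents set no minimum power, so they cannot show whether 87–90% is enough. That judgement belongs to the sponsor.

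**Conclusion.** The concern holds. With the protocol's own SDs, 225 evaluable per lot, identical lots and the 95% CI rule, power is 90.0% for RSV B (stated 94.7%). Overall power is about 87% under independence and at most 90% (stated 93.3%). The risk of missing the primary objective with identical lots is 10–13%, against 6.7% implied.

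The per-antigen results rest on normally distributed log titers with a common SD across lots. The overall range rests on the unstated antigen correlation, but its ceiling does not: no correlation brings it to 93.3%. The likely source, a 90% CI calculation, remains an inference and the finding does not depend on it.

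**What to change.** Recompute Table 4 and the 93.3% sentence in Protocol 9.5 using the 2-sided 95% CI for each pair and the joint distribution of the three pairs. On the stated inputs the entries become 96.8% for RSV A, 90.0% for RSV B and 87.1% overall if independence is kept, with 90.0% as the upper bound. State the calculation method and the antigen correlation assumed.

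The correction covers one table and one sentence. It has no operational cost, needs no change to the SAP and does not in itself alter enrolment. What it does cost is a less favourable power statement, and the sponsor should confirm that the lower figure is acceptable.

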10. SUPPORTING DOCUMENTATION AND OPERATIONAL CONSIDERATIONS

10.1. Appendix 1: Regulatory, Ethical, and Study Oversight Considerations

10.1.1. Regulatory and Ethical Considerations

This study will be conducted in accordance with the protocol and with the following:

- Consensus ethical principles derived from international guidelines, including the Declaration of Helsinki and CIOMS International Ethical Guidelines;
- Applicable ICH GCP guidelines;
- Applicable laws and regulations, including applicable privacy laws.

The protocol, protocol amendments, ICD, SRSD(s), and other relevant documents (eg, advertisements) must be reviewed and approved by the sponsor, submitted to an IRB/EC by the investigator, and reviewed and approved by the IRB/EC before the study is initiated.

Any amendments to the protocol will require IRB/EC approval before implementation of changes made to the study design, except for changes necessary to eliminate an immediate hazard to study participants.

Protocols and any substantial amendments to the protocol will require health authority approval prior to initiation except for changes necessary to eliminate an immediate hazard to study participants.

The investigator will be responsible for the following:

- Providing written summaries of the status of the study to the IRB/EC annually or more frequently in accordance with the requirements, policies, and procedures established by the IRB/EC;
- Notifying the IRB/EC of SAEs or other significant safety findings as required by IRB/EC procedures;
- Providing oversight of the conduct of the study at the site and adherence to requirements of 21 CFR, ICH GCP guidelines, the IRB/EC, European regulation 536/2014 for clinical studies (if applicable), European Medical Device Regulation 2017/745 for clinical device research (if applicable), and all other applicable local regulations.

10.1.1.1. Reporting of Safety Issues and Serious Breaches of the Protocol or ICH GCP

In the event of any prohibition or restriction imposed (ie, clinical hold) by an applicable regulatory authority in any area of the world, or if the investigator is aware of any new information that might influence the evaluation of the benefits and risks of the study intervention, Pfizer should be informed immediately.

In addition, the investigator will inform Pfizer immediately of any urgent safety measures taken by the investigator to protect the study participants against any immediate hazard, and of any serious breaches of this protocol or of the ICH GCP guidelines that the investigator becomes aware of.

10.1.2. Financial Disclosure

Investigators and subinvestigators will provide the sponsor with sufficient, accurate financial information as requested to allow the sponsor to submit complete and accurate financial certification or disclosure statements to the appropriate regulatory authorities. Investigators are responsible for providing information on financial interests during the study and for 1 year after completion of the study.

10.1.3. Informed Consent Process

The investigator or his/her representative will explain the nature of the study, including the risks and benefits, to the participant and answer all questions regarding the study. The participant should be given sufficient time and opportunity to ask questions and to decide whether or not to participate in the trial.

Participants must be informed that their participation is voluntary. Participants will be required to sign a statement of informed consent that meets the requirements of 21 CFR 50, local regulations, ICH guidelines, privacy and data protection requirements, where applicable, and the IRB/EC or study center.

The investigator must ensure that each study participant is fully informed about the nature and objectives of the study, the sharing of data related to the study, and possible risks associated with participation, including the risks associated with the processing of the participant's personal data.

The participant must be informed that his/her personal study-related data will be used by the sponsor in accordance with local data protection law. The level of disclosure must also be explained to the participant.

The participant must be informed that his/her medical records may be examined by Clinical Quality Assurance auditors or other authorized personnel appointed by the sponsor, by appropriate IRB/EC members, and by inspectors from regulatory authorities.

The investigator further must ensure that each study participant is fully informed about his or her right to access and correct his or her personal data and to withdraw consent for the processing of his or her personal data.

The medical record must include a statement that written informed consent was obtained before the participant was enrolled in the study and the date on which the written consent was obtained. The authorized person obtaining the informed consent must also sign the ICD.

Participants must be reconsented to the most current version of the ICD(s) during their participation in the study.

A copy of the ICD(s) must be provided to the participant.

Participants who are rescreened may be required to sign a new ICD as per IRB, local regulations, etc.

